### 3.1.5. Supporting Analyses

The supporting efficacy analyses will include:

- Comparison between the Treatment and Control groups in the of responder rate in ODI at the 1-year visit, where a change ≥15 points is considered a responder
- Comparison between the Treatment and Control groups in the cumulative proportion of responder rate in ODI at the 1-year visit
- Comparison between the Treatment and Control groups in the of responder rate in NRS at the 1-year visit, where a change ≥50% is considered a responder
- Comparison between the Treatment and Control groups in the cumulative proportion of responder rate in NRS at the 1-year visit
- Within group changes in all analyses will also be assessed at the 2-year visit

- Endpoints will be further analyzed by baseline EQ-5D index score
- Health economic outcome measures at the 1- and 2-year visits will be compared to baseline
- Activity monitoring will be collected on a subset of patients and assessed through the 2-year visit and compared to baseline
- Additional ad hoc analyses may also be conducted

#### 3.1.6. Health Economics

Health economic outcome measures to be recorded will include:

- Work status, work-days missed and ability to do their work the year prior to baseline, and at the 1- and 2-year visits
- Health care utilization (office visits, hospital visits, emergency room visits, and other therapies such as physical therapy) the year prior to baseline and at the 1- and 2-year visits

### 3.1.7. Activity Data Collection

Activity data will be collected on a subset of patients who:

- have an activity tracker that they have used regularly for at least three months,
- agree to wear the activity tracker for the duration of the study, and
- agree to have activity data transmitted to be saved in the database.

After signing consent and meeting enrollment criteria, activity data from at least 2 weeks prior to enrollment will be downloaded. Activity data will be collected continuously while the patient is wearing the activity tracker and downloaded periodically by the patient. To help ensure complete data are obtained, a download of the data will also occur at each study visit.

The time period from Baseline through Activation will serve as the Baseline assessment of activity, with the following exceptions:

- Patients in the Treatment group would be expected to be moving less during the healing process post-procedure; therefore, activity data will be excluded between the Implant and Activation visits (approximately 2 weeks).
- Patients in the Control group will have the 2-week time period prior to Activation excluded to align with the timeframe excluded for the Treatment group.

Activity data to be collected include:

- Distance and Number of Steps
- Stationary Time
- Sleep Data

## 3.2. Study Visits and Data Collection Schedule

The study visit schedule is provided in Table 3. The study visit schedule will vary slightly between the groups to account for the Treatment group being implanted after the randomization visit. For the Treatment group, visit timing for all visits will be based on Activation. For the Control group visit timing through the 1-year visit will be based on Randomization. After those in the Control group are implanted, the timing of the remaining visits will be based on the Activation visit.

Visit	Treatment	Control
Informed consent, baseline	$\checkmark$	✓
Randomization (Approx. 14 days post baseline)	$\checkmark$	✓
ReActiv8 implant (Approx. 14 days post randomization)	$\checkmark$	
Activation (Approx. 14 days post implant)	$\checkmark$	
1.5-month (45 ± 14 days)	$\checkmark$	$\checkmark$
3-month (90 ± 30 days)	$\checkmark$	$\checkmark$
6-month (180 ± 30 days)	$\checkmark$	$\checkmark$
1-year (365 ± 60 days)	$\checkmark$	$\checkmark$
ReActiv8 implant (within 60 days of the 1-year visit)		$\checkmark$
Activation (Approx. 14 days post implant)		$\checkmark$
13.5-month (410 ± 14 days)		$\checkmark$
15-month (450 ± 30 days)		$\checkmark$
18-month (540 ± 30 days)	$\checkmark$	$\checkmark$
2-year (730 ± 60 days)	$\checkmark$	$\checkmark$

Table 3: Visit S	chedule with	Recommended	Visit Windows
	Sheadle with	Reconnicitaca	

A summary of the data collection schedule is shown for the Treatment group in Table 4 and for the Control group in Table 5.

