## 1.1. Overall Synopsis of the Clinical Study

This study is a prospective, randomized study comparing ReActiv8 Therapy to Optimal Medical Management (OMM), where OMM means the patient has been managed according to available guideline-directed treatments (e.g., medication, physical therapy, injections), and are intending to continue with their existing course of care during the study. OMM will follow physician treatment practices per the guidelines such that it will be individualized to meet the patient needs. A synopsis of the study in tabular form is shown in Table 1.

All patients who satisfy the enrollment criteria are randomized (1:1) to receive either ReActiv8 (Treatment group) or OMM (Control group).

After randomization, those in the Treatment group will be implanted, and then all patients will be followed at the following timepoints post-implant: 1.5 months, 3 months, 6 months, 1 year, 18 months, and 2 years. After the 1-year visit, patients in the Control group may elect to be implanted with the ReActiv8 device and, in addition to the visits noted above, will have follow-up visits at 13.5 months and 15 months. Patients in the Control group who are not implanted with a ReActiv8 device after the 1-year visit will be exited from the study at that time.

The primary efficacy endpoint is a comparison of mean change in Oswestry Disability Index (ODI) at 1 year compared to baseline.

Secondary and tertiary endpoints will be assessed at the 1-year visit compared to baseline, including change in Numerical Rating Scale (NRS) Pain score, a composite of change in ODI and change in NRS Pain score, change in EQ-5D Quality of Life, Percent Pain Relief, Subject Global Impression of Change (SGIC), and Treatment Satisfaction.

Related adverse events (AEs) and all serious adverse events (SAEs) will be reported from enrollment through study exit.

Study Purpose	To compare the effectiveness of ReActiv8 to OMM for the treatment of intractable chronic low back pain (CLBP).		
Indications for Use	The ReActiv8 System is indicated for bilateral stimulation of the L2 medial branch of the dorsal ramus as it crosses the L3 transverse process as an aid in the management of intractable chronic low back pain associated with multifidus muscle dysfunction, as evidenced by imaging or physiological testing in adults who have failed therapy including pain medications and physical therapy and are not candidates for spine surgery.		
Study Device	ReActiv8 System		

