### 4.2. Missing Data and Sensitivity Analyses

The primary and secondary efficacy endpoints will be assessed in the population of all randomized patients with at least one follow-up visit at or before the 1 Year visit, For the primary and secondary efficacy endpoints, mixed-effect repeated measure (MMRM) analyses will be conducted utilizing all available data through 1 Year. Additional sensitivity analyses will be conducted to assess the impact of missing data.

As a supporting analysis, the primary and secondary efficacy endpoints will be summarized in the completer cohorts consisting of all patients with both baseline and 1 Year data available. This will be summarized as the arithmetic mean change from baseline rather than the model-based estimation used for the primary analysis.

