### 5.8. Defining the Primary Estimand

Further refinement of primary estimand,  $\delta_T - \delta_C$ , and implications for handling missing data and clinical status measures after relevant 'intercurrent' events are now discussed in the context of FDA Guidance E9(R1). The primary estimand is defined as the *treatment group difference in* (adjusted) mean changes from baseline to 1 Year among patients who start their randomized treatment and continue on that treatment throughout the 1 Year follow-up period.

Reasons for missing after initial treatment initiation for patients with at least one follow-up visit (at Months 1.5, 3 6, and/or 1 Year) will be categorized as:

- Withdrawal due to lack of effectiveness
- Crossover from control to ReActiv8 due to lack of effectiveness
- Withdrawal due to removal of ReActiv8 for reasons other than lack of effectiveness (e.g., to obtain an MRI)
- Withdrawal due to adverse event
- Missing due to loss-to-follow-up with no known reason

Randomized patients who do not initiate a study treatment or do not have any follow-up data through 1 Year will be categorized as:

- Randomized to ReActiv8 but withdrawn prior to implant
- Randomized to ReActiv8 but withdrawn before any follow-up visit
- Randomized to OMM but withdrawn before any follow-up visit

E9(R1) sets up the argument for specifying clinically meaningful estimands as follows:

It remains undisputed that randomization is a cornerstone of controlled clinical trials and that analysis should aim at exploiting the advantages of randomization to the greatest extent possible. However, the question remains whether estimating an effect in accordance with the ITT principle always represents the treatment effect of greatest relevance to regulatory and clinical decision making. The framework outlined in this addendum gives a basis for describing different treatment effects and some points to consider for the design and analysis of trials to give estimates of these treatment effects that are reliable for decision-making.

Relevant comments from E9(R1) include:

- Discontinuation of randomized treatment represents an intercurrent event to be addressed in the precise specification of the trial objective through the estimand. Study withdrawal gives rise to missing data to be addressed in the statistical analysis.
- Switching treatment represents an intercurrent event, and the clinical question of interest in respect to that event should be clear.

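### A patient randomized to ReActiv8 but never activated has no date for any outcome visit, so some losses specific to the Treatment arm can leave no post-baseline ODI, and no all-randomized analysis is planned

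*Protocol*

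**What the plan says.** **Visit clock.** Protocol 3.2 sets one starting point per arm: "For the Treatment group, visit timing for all visits will be based on Activation", and "For the Control group visit timing through the 1-year visit will be based on Randomization". The synopsis table in Protocol 1.1 agrees, but the narrative of 1.1 says something else: "After randomization, those in the Treatment group will be implanted, and then all patients will be followed at the following timepoints post-implant". Neither gives timing for a Treatment patient who is never activated.

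**Other contacts.** ODI, NRS and EQ-5D are not collected at unscheduled visits (Protocol Table 4 and 5.11). After an explant, Protocol 5.12 asks only for device information and adverse events, and 7.1 keeps the patient in the study for a minimum of 30 days for safety reporting.

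**Analysis sets.** SAP 4.2 assesses the primary and secondary endpoints in "all randomized patients with at least one follow-up visit at or before the 1 Year visit". SAP 5.8 instead defines a Full Analysis Set (FAS). It admits Treatment patients only if they were implanted and have a follow-up assessment, and Controls if they have a follow-up assessment. The completer cohort in SAP 4.2 needs 1-year data. SAP 5.8 lists a category "Randomized to ReActiv8 but withdrawn prior to implant". SAP 5.2 counts the randomized patients left out but does not analyse them.

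**The concern.** Surgery that is refused, surgery that cannot go ahead, and a complication that removes the device before Activation are events after randomization. Under the protocol they can happen in year 1 only in the Treatment arm. If these patients have no dated outcome visit, they can disappear from the efficacy data without anyone breaking the protocol. Controls keep a dated visit from Randomization whatever happens to their care.

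The patients lost this way had no device benefit. Removing them from one arm of an open-label comparison would tend to raise the estimated effect and weaken the protection that randomization gives. Outcomes that were never collected cannot be observed later.

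**Working it through.** **1. When the first outcome is due.** Inputs from Protocol Table 3: implant about 14 days after Randomization, Activation about 14 days after implant, first ODI visit at 45 ± 14 days on each arm's own clock.

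- Treatment: 14 + 14 + 45 = day 73 after Randomization (window 59 to 87).
- Control: day 45.
- The period in which a patient can leave with no post-baseline ODI is about 73 − 45 = 28 days longer in Treatment.

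**2. Explant before Activation.** Implant is near day 14 and Activation near day 28. With explant in between and the 30-day minimum of Protocol 7.1, exit is possible from about day 14 + 30 = 44 to day 28 + 30 = 58. All of that range lies before day 59, when the window for the first Treatment ODI would have opened. Such a patient can exit in full compliance with no post-baseline ODI.

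**3. Who is in which set.**

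| Treatment-arm patient | Dated ODI visit | SAP 4.2 population | Completers | FAS (SAP 5.8) |
|---|---|---|---|---|
| Never implanted, not seen | No | Out | Out | Out |
| Never implanted, seen anyway | No | In | In if seen at 1 year | Out |
| Explanted before Activation, not seen | No | Out | Out | Out |
| Explanted before Activation, seen anyway | No | In | In if seen at 1 year | In |
| Fails after a first follow-up assessment | Yes | In | In if 1-year data exist | In |

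In the last row, withdrawal for lack of effectiveness or an adverse event gets baseline carried forward (BOCF), with last observation carried forward as sensitivity. Removal of the device for other reasons is handled under missing at random (SAP 5.8). A patient explanted before Activation because of an adverse event is not reached by the BOCF rule unless a follow-up assessment exists.

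Rows 2 and 4 show two separate mechanisms. The missing clock is what keeps the explanted patient out of the FAS. For the never-implanted patient, the implant condition would do so even if visits took place.

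**4. The plan's own sample size.** Protocol 3.1.1.2 and SAP 3.2 assume improvements of 18.2 and 12.2 (difference 6.0), SD 15, two-sided 5% and 80% power. The normal formula, 2 × (1.960 + 0.842)² × 15² / 6.0² = 98.1, gives 99 per arm, 198 in total. The t-test version gives 200. The stated 204 is consistent with both.

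**5. Size.** Neither document gives the share p of the Treatment arm never activated. I assume 2%, 5% and 10% of 230 / 2 = 115 patients. Let m be their mean 1-year improvement.

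- All-randomized difference = (1 − p) × 18.2 + p × m − 12.2
- Overstatement from leaving them out = p × (18.2 − m)

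| p (patients) | m = 12.2: difference | Overstatement | m = 0: difference | Overstatement |
|---|---|---|---|---|
| 2% (about 2) | 5.88 | 0.12 | 5.64 | 0.36 |
| 5% (about 6) | 5.70 | 0.30 | 5.09 | 0.91 |
| 10% (about 12) | 5.40 | 0.60 | 4.18 | 1.82 |

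**The case against.** The other side has several good points.

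- **The estimand is declared.** SAP 5.8 targets patients who start and stay on their randomized treatment, and counting from Activation gives each device patient a comparable period of exposure. That stands as a choice for the primary analysis. It does not explain the absence of any all-randomized sensitivity analysis, or the different population in SAP 4.2.
- **Follow-up is not forbidden.** Tables 3 and 4 assign the visits to the whole Treatment arm, Protocol 5 treats windows as guidance and a missed visit as a deviation, and SAP 4.3 analyses data by the visit recorded in the database. This is true, but guidance around a date that does not exist gives the site no date.
- **Adding visits does not change the FAS test for never-implanted patients.** This stands. The fix must therefore also cover the analysis.
- **Controls with no follow-up are excluded too.** This also stands, so the net direction of bias is likely rather than certain.

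A reader might infer that device-arm failures in general drop out of every efficacy set. The documents do not support that: failures after a first follow-up assessment stay in the FAS. A reader might also infer that no later analysis could bring the lost patients back. Baseline ODI is collected from everyone before randomization, so an all-randomized BOCF analysis is possible. It is only a weaker substitute for observed outcomes.

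**Conclusion.** The point holds in a limited form. The protocol gives no outcome-visit date to a Treatment patient who is never implanted or is explanted before Activation. Followed as written, it allows a loss after randomization that is specific to that arm and leaves no post-baseline ODI. The FAS implant condition adds a second, independent exclusion that applies to Treatment only.

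On assumed rates of 2% to 10%, the planned 6.0-point difference would be overstated by 0.1 to 0.6 points if these patients change like Controls, and by 0.4 to 1.8 points if they do not change. The upper figure is 1.82 / 6.0 = 30% of the planned effect. A reader might take it as the expected bias, but it needs both a 10% rate and zero change, and neither is in the documents. Ten percent of one arm would be about 12 of the 230 − 204 = 26 patients allowed for attrition in both arms together. Since eligibility requires patients to be on medical management already, the Control-like range is a natural assumption for those never implanted.

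**What to change.** 1. **Protocol 3.2 and Table 3.** State that a Treatment patient with no Activation by the date the Control 1.5-month visit would fall (day 45 after Randomization), or explanted before Activation, has ODI, NRS, EQ-5D and adverse events collected at 1.5, 3, 6 and 12 months from Randomization. State that non-implantation alone is not study withdrawal, and how visits are timed if Activation happens later.
2. **Reconcile the texts.** Protocol 1.1 and 3.2 must agree on the visit clock, and SAP 4.2 and 5.8 on the primary population.
3. **SAP.** Add a sensitivity analysis of all randomized patients in their assigned arms, using these observed data, with BOCF where no follow-up exists.

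The declared primary estimand can stay. The change concerns data collection and analysis only, not treatment. The cost is protocol and SAP wording plus four questionnaire contacts for each affected patient, about 2 to 12 patients on the assumed rates. Protocol 7 already allows electronic completion. Some of these patients will decline, and the all-randomized estimate may be slightly less favourable to the device.

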#### Table 4: Summary Data Collection Schedule – Treatment Group

	Informed Consent & Baseline	Randomization	ReActiv8 Implant & Activation	1.5 Month Visit	3-Month Visit	6-Month Visit	1-Year Visit	18-Month Visit	2-Year Visit	Unscheduled Visit
Screening Data & Physical Exam	✓									
MRI	✓									
Multifidus Dysfunction Assessment	~									
DASS 21	✓									
ODI	✓			✓	$\checkmark$	✓	$\checkmark$	~	✓	
Low Back Pain NRS	×			✓	$\checkmark$	✓	✓	✓	✓	
EQ-5D	$\checkmark$			$\checkmark$	$\checkmark$	✓	$\checkmark$	~	✓	
Low Back Pain Description	~			✓	$\checkmark$	✓	$\checkmark$	✓	✓	
Leg Pain Description and NRS	$\checkmark$			✓	$\checkmark$	✓	$\checkmark$	✓	✓	
Percent Pain Relief				✓	$\checkmark$	✓	$\checkmark$	✓	✓	
SGIC				$\checkmark$	$\checkmark$	✓	$\checkmark$	✓	✓	
Treatment Satisfaction				✓	$\checkmark$	✓	$\checkmark$	✓	✓	
Health Care Utilization	$\checkmark$						$\checkmark$		✓	
Work Status Evaluation	~						$\checkmark$		✓	
Activity Data Download (if applicable)	~		✓	✓	$\checkmark$	✓	$\checkmark$	$\checkmark$	✓	
Pain Treatments Log	~			✓	$\checkmark$	✓	$\checkmark$	✓	✓	✓
Related AEs & All SAEs			✓	$\checkmark$	$\checkmark$	✓	$\checkmark$	~	✓	✓
Device Measurements Download			✓	✓	$\checkmark$	✓	$\checkmark$	$\checkmark$	✓	$\checkmark$

#### Table 5: Summary Data Collection Schedule – Control Group

	Informed Consent & Baseline	Randomization	1.5 Month Visit	3-Month Visit	6-Month Visit	1-Year Visit	ReActiv8 Implant & Activation	13.5 Month Visit	15-Month Visit	18-Month Visit	2-Year Visit	Unscheduled Visit
Screening Data & Physical Exam	~											
MRI	~											
Multifidus Dysfunction Assessment	~											
DASS 21	~											
ODI	~		✓	$\checkmark$	✓	$\checkmark$				✓	$\checkmark$	
Low Back Pain NRS	~		✓	$\checkmark$	✓	✓				✓	✓	
EQ-5D	~		✓	$\checkmark$	✓	$\checkmark$				✓	$\checkmark$	
Low Back Pain Description	✓		✓	$\checkmark$	✓	✓				✓	$\checkmark$	
Leg Pain Description and NRS	~		✓	$\checkmark$	✓	$\checkmark$				✓	$\checkmark$	
Percent Pain Relief			✓	$\checkmark$	✓	✓				✓	$\checkmark$	
SGIC			✓	$\checkmark$	✓	$\checkmark$				~	$\checkmark$	
Treatment Satisfaction			✓	$\checkmark$	✓	✓				✓	$\checkmark$	
Health Care Utilization	~					$\checkmark$					$\checkmark$	
Work Status Evaluation	✓					✓					✓	
Activity Data Download (if applicable)	~		✓	$\checkmark$	✓	$\checkmark$	$\checkmark$			✓	$\checkmark$	
Pain Treatments Log	✓		✓	$\checkmark$	✓	✓		$\checkmark$	$\checkmark$	✓	$\checkmark$	$\checkmark$
Related AEs & All SAEs			✓	$\checkmark$	✓	✓	$\checkmark$	$\checkmark$	~	~	~	$\checkmark$
Device Measurements Download							✓	✓	✓	✓	✓	$\checkmark$

The contents of this document are confidential and are not to be reproduced or made available to third parties without prior consent
from Mainstay Medical and are not to be used in any unauthorized way.Page 25 of 47Document Number 980012, Rev. D11-JAN-2024

### 3.3. Patient Selection

#### 3.3.1. Inclusion Criteria

- 1. Indicated for the ReActiv8 System
  - Age ≥21 years
  - Evidence of lumbar multifidus muscle dysfunction
  - Intractable Chronic Low Back Pain that has persisted >6 months prior to enrollment, resulting in pain most of the days in the 12 months prior to enrollment
  - Failed therapy including pain medications and physical therapy
  - Not a candidate for spine surgery
- 2. Low Back Pain NRS of ≥6 and ≤9
- 3. Oswestry Disability Index score  $\geq$  30 and  $\leq$  60
- 4. Willing and capable of giving Informed Consent.
- 5. Able to comply with this protocol
- 6. On Optimal Medical Management per the Investigator

#### 3.3.2. Exclusion Criteria

- 1. Contraindicated for the ReActiv8 System
  - Unable to operate the ReActiv8 System
  - Unsuitable for ReActiv8 implant surgery
- 2. BMI > 35
- 3. Back Pain characteristics:
  - a. Any surgical correction procedure for scoliosis at any time, or a current clinical diagnosis of moderate to severe scoliosis (Cobb angle ≥25°)
  - b. An independent MRI assessment identifying a pathology that is likely the cause of the CLBP and is amenable to surgery
- 4. Leg pain described as being worse than back pain, or radiculopathy (neuropathic pain) below the knee
- 5. Surgical or other procedures exclusions:
  - a. Any previous back surgery (e.g., laminectomy, discectomy, spinal fusion) at or below segmental level T8
  - b. Any previous thoracic or lumbar sympathectomy
  - c. Any lumbar rhizotomies within the past 12 months
  - d. Any lumbar nerve blocks within the past 30 days
  - e. Any previous or existing neuromodulation devices (e.g., drug pump, spinal cord stimulation, and/or peripheral nerve stimulation)
- 6. Other clinical conditions:
  - a. Pregnant or planning to be pregnant in the next 12 months
  - b. Any condition unrelated to CLBP such as muscle wasting, muscle atrophy, or progressive neurological disease which, in the opinion of the Investigator, could limit physical movement or compliance with the protocol, or interfere with the assessment of efficacy

- c. Evidence of an active disruptive psychological or psychiatric disorder or other known condition significant enough to impact perception of pain, compliance with intervention and/or ability to evaluate treatment outcome (e.g., active depression, bipolar disease, Alzheimer's disease) as determined by the Investigator in consultation with a psychologist or psychiatrist, as appropriate
- d. An opioid addiction or drug-seeking behavior, as determined by the Investigator
- e. Any active malignant disease
- f. Any active infection in the vicinity of the implant site or any systemic infection
- g. Poorly controlled diabetes (Type I or Type II) determined by HbA1c >8
- 7. General exclusions:
  - a. Current smoker
  - b. Current or planned participation in any other clinical trial during the study
  - c. A condition currently requiring or likely to require use of MRI or diathermy
  - d. Life expectancy less than one year
  - e. A pending or approved financial compensation claim (e.g., worker's compensation claim, long term disability claims, injury claim under litigation)

